5. INITIAL EVALUATION

5.1. BASELINE CHARACTERISTICS

5.1.1. Biological factors

- Anthropological: age, sex, weight, height and body mass index.
- Sex-specific factors of women's cardiovascular risk: menarche age, number of pregnancies, gestational diabetes, early menopause, polycystic ovary syndrome, presence and number of miscarriages, use of hormonal replacement therapy (yes/no, duration), fertility treatments, use of hormonal contraceptives, history of eclampsia or pre-eclampsia, history of breast or endometrial cancer.
- Vital signs: blood pressure (SBP, DBP) and heart rate.
- Risk factors: hypertension, diabetes, hyperlipidemia, LDL, HDL, total cholesterol, triglycerides, lipoprotein(a), uric acid, tobacco and alcohol consumption, chronic alcoholism, HbA1c level, waist circumference, familiar history of premature coronary artery disease or familiar hypercholesterolemia. Pattern of food consumption and practice of physical activity (this will be measured using

questionnaire MEDAS and IPAQ which will be described in the followings sections).

- Comorbidities: prior coronary artery disease (acute or chronic coronary syndrome), prior percutaneous coronary intervention, prior CABG, prior cerebrovascular disease (transient ischemic attack, ischemic stroke), peripheral vascular disease, heart failure, chronic kidney disease, COPD, Obstructive sleep apnea/hypopnea syndrome (OSAHS), atrial fibrillation, autoimmune disorders, anemia, depression (diagnosis of major depressive disorder), anxiety (diagnosis of generalized anxiety disorder) and Charlson Comorbidity Index (CCI).¹⁵

5.1.2. Disease related factors

AMI features:

- Type of MI (STEMI/NSTEMI)
- Number of diseased vessels
- BARI segment responsible of AMI
- Left ventricular ejection fraction at discharge (LVEF) before discharge (typically by echocardiography)
- Killip class (on admission, “maximal”)
- In-hospital complications (heart failure, bleeding, arrhythmias, cardiogenic shock).

In-hospital management:

- Reperfusion rates and times (for STEMI)
- Patients receiving coronary angiography (for non-STEMI) and time since diagnosis to coronary angiography
- Type of coronary revascularization
- Coronary revascularization rates and completeness
- Admission to the coronary unit
- Length of hospital stay

5.1.3. Socioeconomic factors

- Social factors: ethnic group, educational level, marital status/living arrangements, role of primary caregiver and overload, country of birth, zip code.

- Economic factors: income category, employment status, type of contract (part-time or full-time), work conciliation.
- Quality of life (SF-12¹⁶), Spanish version.⁷¹

5.1.4. Psychological factors

- Anxiety and Depression (HADS⁷²), Spanish version.⁷³

5.1.5. Gender issues

- Domestic and care workloads and intensity, frequency and duration of care: time of care and domestic work and intensity, frequency and duration of care, as well as the distribution of care (CUIDAR-SE Questionnaire).
- Zarit Caregiver Burden Interview,⁷⁴ Spanish version⁷⁵

5.2. SECONDARY PREVENTION RECOMMENDATIONS

5.2.1. PHARMACOLOGICAL TREATMENTS

- Secondary prevention strategies and medications (drugs)
 - o Antiplatelets: Aspirin and P2Y₁₂ inhibitors (including type)
 - o Lipid-lowering therapies (statins, ezetimibe, PCSK9)
 - o RAASi
 - o Betablockers
 - o Glucose control medications [SGLT2 inhibitors, GLP-1 agonists...]
- Prescription pattern: Total number of daily intakes, dose of each medication, total number of medications, use of injectable drugs, past difficulties regarding type of therapy.

5.2.2. Referral To Cardiac Rehabilitation/Secondary Prevention Program

- Prescription pattern: Recommendation and scheduling to attend and participate in a structured program of cardiac rehabilitation/secondary prevention education
- Adherence to the cardiac rehabilitation program
 - o Number of attended sessions divided by the number of sessions prescribed.
 - o ¿Achieve goals of target heart rate? TBD

5.2.3. Diet Recommendations

Current cardiovascular prevention guidelines recommend adopting a diet based on farm products and reducing foods of animal origin, together with the following recommendations:⁷⁶

- The consumption of saturated fats should not exceed 10% of total daily energy intake. Likewise, it is recommended to replace these with fats that contain polyunsaturated and monounsaturated fatty acids.
- Replace carbohydrates in the diet with whole grain products (with whole grain cereals).
- Trans fats should be minimized as much as possible, especially those from processed foods, whose consumption is totally discouraged.
- Reduce salt intake to <5 g per day.
- Consume 30-45 g of fiber per day, preferably from whole grain cereals.
- The intake of more than 200 grams of fruit per day (2 or 3 meals per day) is recommended.
- Eat more than 200 grams of vegetables a day (2 or 3 meals a day).
- Reduce the consumption of red meat to a total of 150-500 grams per week, especially processed meats.
- The consumption of fish is recommended 1 or 2 times a week, particularly the consumption of fish with essential fatty acids.
- Consume 30 grams of unsalted nuts per day.
- Reduce alcohol consumption to a maximum of 100 grams per week.
- The consumption of sugary drinks such as soft drinks or fruit juices is discouraged.

5.2.4. Physical Activity Recommendations

- Prescription pattern: current cardiovascular prevention guidelines recommend performing moderate-intensity physical activity for 30 minutes a day 5 or 7 days a week (a total of 150-300 minutes a

week) or performing 75 minutes of vigorous activity 1 or 2 days a week (a total of 75-150 minutes a week) for cardiovascular risk reduction⁷⁶.

5.3. OUTCOMES

All outcomes will be compared between men and women.

OUTCOME DEFINITIONS

5.3.1. Co-Primary outcomes

- **Pharmacological primary endpoint:** outcome of adherence to pharmacological therapies (MMAS-8) 12 months after discharge.
- **Non-pharmacological primary endpoint:** Composite outcome of adherence to non-pharmacological secondary CV prevention recommendations 12 months after discharge, including diet, physical activity and participation in cardiac rehabilitation programs.

Adherence will be defined as compliance with at least 80% of each of the CV prevention recommendations separately: medications, cardiac rehabilitation program, diet and physical activity. This outcome is defined as an all-or-nothing endpoint with a binary response. These outcomes are defined as an all-or-none endpoint with a binary response.

5.3.2. Secondary outcomes.

- **Pharmacological primary endpoint:** outcome of adherence to pharmacological therapies (MMAS-8) 6 months after discharge.
- **Non-pharmacological primary endpoint:** Composite outcome of adherence to non-pharmacological secondary CV prevention recommendations 6 months after discharge, including diet, physical activity and participation in cardiac rehabilitation programs.

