End-points. Primary end-point: composite outcome of adherence to all secondary CV prevention recommendations 12 months after discharge, including pharmacological therapies, diet, physical activity and participation in cardiac rehabilitation programs. Secondary end-points: adherence to all secondary CV prevention recommendations at 6 months, percentage of patients achieving optimal control of all individual CV risk factors, composite clinical endpoint at 12 months: all-cause death, all-cause rehospitalization, and all-cause emergency department visits, among others.

Statistical analysis. A logistic regression models will be used to evaluate differences in the primary outcome between women and men, as well as in other outcomes. All subjects will be assumed to have a fixed follow-up (12 ± 1 month). Multivariate adjusted models will be used to address any potential confounding in the associations between sex and each of the outcomes. Covariates will be selected based on their pre-defined clinical value and the unbalances observed across groups in the univariate analyses.

Sponsor: Sociedad Española de Cardiología

Funding: ORGANON (Unrestricted grant)

Principal Investigator: [name], PhD

Executive Committee: [name], PhD; [name] [name], PhD, [name] [name], PhD, [name], PhD; [name], PhD

Scientific Committee: [name], PhD; [name] [name], PhD, [name] [name], PhD; [name] [name], PhD, [name], PhD; [name], PhD; [name] [name], PhD; [name] [name], PhD; [name] [name], PhD;

Clinical sites (25)

	C. Autónoma	Hospital	Población
1	Andalucía	Hospital Universitario Virgen Macarena	Sevilla
2	Andalucía	Hospital Universitario Virgen de la Victoria	Málaga
3	Aragón	Hospital Universitario Lozano Blesa	Zaragoza
4	Asturias	Hospital Universitario Central de Asturias	Oviedo
5	Baleares	Hospital Universitari Son Espases	Palma de Mallorca
6	C. La Mancha	Complejo Hospitalario de Toledo	Toledo
7	C. La Mancha	Complejo Hospitalario Universitario de Albacete	Albacete
8	C. León	Hospital Clínico Universitario de Salamanca	Salamanca
9	C. León	Complejo Asistencial Universitario de León	León
10	C. Madrid	Hospital Universitario Fundación Alcorcón	Alcorcón
11	C. Madrid	Hospital Universitario 12 de Octubre	Madrid
12	C. Valenciana	Hospital General Universitario de Alicante	Alicante
13	C. Valenciana	Hospital Clínico Universitario de Valencia	Valencia
14	Canarias	Hospital Universitario de Gran Canaria [name] (*)	Las Palmas de Gran Canaria

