3. OBJECTIVES

General objective. To evaluate if there are differences in the level of adherence to recommended secondary prevention therapies (pharmacological and non-pharmacological) between women and men surviving a type 1 AMI (with obstructive CAD), its potential consequences, and the potential factors related to that difference, if present.

Specific objectives. To compare between women and men:

- 1) The adherence to recommended secondary prevention therapies at 6 months and 12 months measured as the
 - 1a. Proportion of patients adherent to all recommended pharmacological secondary prevention therapies at 6 and 12 months
 - 1b. Proportion of patients adherent to all recommended non-pharmacological secondary prevention therapies at 6 and 12 months
- 2) The relationship of the adherence with control of risk factors, clinical outcomes, and use of healthcare resources
 - 2a. The proportion of patients with optimal control of all cardiovascular risk factors at 6 and 12 months
 - 2b. The incidence of clinical outcomes at 6 and 12 months
 - 2c. The cumulative use of healthcare resources and cost after discharge
- 3) To assess the factors associated with non-adherence to recommended secondary prevention therapies, with special emphasis to socioeconomic factors and gender issues.

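### The protocol names two incompatible primary endpoint sets, and its sample size covers one test of one composite, so power for the two co-primaries is not established

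*Protocol*

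**What the plan says.** - **Summary, End-points:** one primary, "Primary end-point: composite outcome of adherence to all secondary CV prevention recommendations 12 months after discharge", covering drugs, diet, physical activity and rehabilitation. The 6-month version is secondary: "Secondary end-points: adherence to all secondary CV prevention recommendations at 6 months".
- **Section 5.3, Outcome metrics:** again a single primary, the 12-month all-or-nothing composite over the same four components.
- **Section 5.3.1, "5.3.1. Co-Primary outcomes":** two primaries, namely "outcome of adherence to pharmacological therapies (MMAS-8) 12 months after discharge" and "Composite outcome of adherence to non-pharmacological secondary CV prevention recommendations 12 months after discharge". The closing text describes the all-or-none rule twice in consecutive sentences, once for a single outcome and once for several.
- **Sections 5.3.2 and 5.3.3:** the 12-month all-component composite is in neither. Its 6-month version is exploratory, and at 12 months only its individual components are listed.
- **Section 3, Objectives:** the general objective is undivided ("the level of adherence to recommended secondary prevention therapies (pharmacological and non-pharmacological) between women and men"). Sub-objectives 1a ("Proportion of patients adherent to all recommended pharmacological secondary prevention therapies at 6 and 12 months") and 1b ("Proportion of patients adherent to all recommended non-pharmacological secondary prevention therapies at 6 and 12 months") follow the co-primary split.
- **Section 6:** sizes the all-or-none composite primary outcome, in the singular and without listing its components. It uses 42% in women and 52% in men, α 0.05 and β 0.20, giving 410 per group (820 in total), then 984 with 20% loss, rounded to 1000.

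**The concern.** The primary endpoint is fixed twice, differently, and no text ranks one version above the other. An analysis plan can agree with at most one of them. Because the sets classify patients differently, the same data could support different conclusions about women and men depending on which section is followed, and the choice could be made after results are seen.

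The sample size inherits the problem. It supports one test of one endpoint, most naturally the all-component composite. If 5.3.1 governs, the study has been sized on an endpoint that its outcome lists no longer contain, and neither co-primary has a stated rate, difference or power.

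**Working it through.** **1. What was sized.** Inputs from section 6: p₁ = 0.42, p₂ = 0.52, d = 0.10, α = 0.05, power 0.80. Sidedness is not stated; two-sided is tried. Mean rate p̄ = 0.47.

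- Uncorrected: n = [1.960·√(2·0.47·0.53) + 0.842·√(0.42·0.58 + 0.52·0.48)]² / 0.10² = (1.383 + 0.591)² / 0.01 = 389.9.
- Continuity-corrected: n = (389.9/4)·[1 + √(1 + 4/(389.9·0.10))]² = 409.6, so 410 per group and 820 in total, as stated.

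The one-sided calculations (307, or 327 corrected), the unpooled two-sided (388) and the arcsine (390) do not give 410. The figure is therefore one comparison of one pair of rates.

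**2. Power at the expected evaluable number.** 1000 × 0.80 / 2 = 400 per group.

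- Corrected: Φ{[(0.10 − 1/400)·√400 − 1.383] / √0.4932} = Φ(0.807) = 79.0%. At 410 it is 80.0%.
- Uncorrected: Φ{[0.10·√400 − 1.383] / √0.4932} = Φ(0.878) = 81.0%.

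**3. What this implies for the co-primaries.** Anyone who meets the composite meets both co-primaries. If 42% and 52% are the composite rates, they are therefore only lower bounds for each co-primary, and the difference between the sexes on each is unspecified.

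The three splits below are **assumptions**, not protocol figures. Each keeps the composite at 42% versus 52%:

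- A: equal independent halves, √0.42 and √0.52.
- B: equal halves with correlation 0.5, solving p² + 0.5·p(1 − p) = 0.42 or 0.52.
- C: unequal independent parts, 0.70 × 0.60 = 0.42 and 0.80 × 0.65 = 0.52.

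Power with 400 per group, corrected (uncorrected):

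| Split | Rates, women v men | Each at 0.05 | Both at 0.05 | Either, 0.025 each |
|---|---|---|---|---|
| A | 64.8% v 72.1% on each | 57% (60%) | 33% (37%) | 71% (74%) |
| B | 54.4% v 63.6% on each | 73% (75%) | 59% (62%) | 78% (80%) |
| C | drugs 70% v 80%; non-drug 60% v 65% | 89% (91%); 28% (31%) | 25% (28%) | 86% (88%) |

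The last two columns were simulated with 400,000 studies per case. Where the parts are independent they can be checked by hand. For A, both: 0.574 × 0.574 = 0.33. For C, both: 0.891 × 0.283 = 0.25. For C, either: the powers at 0.025 are 0.829 and 0.196, so 1 − 0.171 × 0.804 = 0.86.

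**The case against.** The contradiction itself has no answer in the protocol. The objections concern its weight.

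- **The splits are invented, and the rule for success may sit in the analysis plan.** Both points are right. Power for both co-primaries looks poor in all three splits, while an either-wins rule with α halved gives 71% to 86% corrected. The table shows only that power depends on rates the protocol does not give and on a rule that may sit elsewhere. It does not show that the study is underpowered.
- **The 79% rests on an inferred continuity correction.** This is also right. Section 6 does not state one, and the planned logistic regression is closer to the uncorrected 81%. The gap from 80% is about one point either way and is not the issue.
- **The 400 against 410 shortfall is a separate matter.** It arises because 984 is 820 × 1.2, whereas 820/0.8 = 1025. It enters here only because restated power should use the expected evaluable number.
- **The study is observational and collects every component under either version.** True, which is why the repair is cheap. But the protocol states hypotheses, α and power, and an unsettled primary endpoint undermines all three.

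An analysis plan that is not shown could supply a multiplicity rule. It could not agree with both primary sets.

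**Conclusion.** The concern holds and must be fixed. The Summary and Outcome metrics name one primary endpoint, section 5.3.1 names two different ones, and the single composite has no place in the 12-month outcome lists. The 6-month composite is also placed in two tiers.

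The stated sample size is correct for one two-sided, continuity-corrected test of 42% versus 52%. At 400 evaluable per group that test has 79.0% power, or 81.0% uncorrected. Power for the co-primaries is not established and could lie above or below 80%. The range of 28% to 89% for a single co-primary rests wholly on the assumed splits. Reading the sized endpoint as the all-component composite is the most natural interpretation, but section 6 does not say so.

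**What to change.** Issue a dated amendment before outcome data are examined. Name one primary set and use it in the Summary, section 3, section 5.3.1, Outcome metrics and section 6. There are two routes:

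- **(a) Single composite.** List the 12-month all-component composite in 5.3.1 and in the objectives, move the two co-primaries to key secondary, and restate power at 400 evaluable per group: about 79% with the correction that reproduces 410, or 81% without it, saying which is used. *Cost:* the co-primaries lose primary status. On the corrected basis, 80% needs 410 evaluable per group.
- **(b) Co-primaries.** Amend the Summary and Outcome metrics, state or cross-refer to the rule on whether either or both must succeed, and restate power from endpoint-specific rates at the expected evaluable number. *Cost:* those rates must be found, and the resulting power may be less favourable.

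Under either route, state in section 6 which components the sized composite contains, and give the 6-month all-component composite one tier. The predictive model in section 6 uses a further all-or-nothing composite that omits aspirin and cardiac rehabilitation; align it, or label it as a different outcome. The whole change is wording and a power statement, with no extra data collection.

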5.3.3. Pre-defined exploratory outcomes

- Composite outcome of adherence to all secondary CV prevention recommendations 6 months after discharge (all-or-none composite outcome with a binary response)

- Percentage of patients achieving optimal (guidelines-recommended) control of all individual CV risk factors (LDL-cholesterol levels, blood pressure levels, HbA1c levels, smoking, levels of physical activity/sedentary life)
- 12-month incidence of the composite clinical endpoint: All-cause death, all-cause rehospitalization, and all-cause emergency department visits
- Use of healthcare resources at 12 months, including: days hospitalized (re-hospitalizations), number of ED visits, number of cardiac rehabilitation sessions, number of outpatient specialist visits, and number of urgent PCI procedures).
- Assessment of the main predictors of adherence with secondary prevention recommendations in women (biological, disease-related, pharmacological, socio-economic, psychological, gender)
- Composite outcome of adherence to all secondary pharmacological CV prevention recommendations 12 months after discharge, using pharmacy dispensation records.
- In addition, data on changes in dose or drug will be collected to analyze their influence on adherence.
- Evaluation of each individual components of the composite of adherence to secondary CV prevention recommendations 6 and 12 months after discharge (these recommendations will be given to all patients at discharge):
 - Pharmacological therapies
 - Diet
 - Physical activity and
 - Participation in cardiac rehabilitation programs
- Percentage of patients achieving optimal (guidelines-recommended) control of all individual CV risk factors:
 - LDL-cholesterol levels
 - Blood pressure levels
 - HbA1c levels
 - BMI
 - Smoking

- Levels of physical activity/sedentary life
- Diet
- Composite endpoint of cardiovascular death, rehospitalization, and emergency department visits for cardiovascular causes, and urgent coronary revascularization.
- Effect of delays on return to work on adherence to cardiac rehabilitation and other secondary prevention measures.

OUTCOME METRICS

- **Primary endpoint:** Composite outcome of adherence to all secondary CV prevention recommendations at 12 months after discharge. The composite is built as an all-or-nothing response to an adherence $\geq 80\%$ in all prescribed components of the endpoint: pharmacological therapies (MMAS-8), diet, physical activity and participation in a cardiac rehabilitation program. Adherence will be defined as having at least 80% compliance with all CV prevention recommendations; drugs, cardiac rehabilitation program, diet and physical activity)
- Measurement of adherence to secondary prevention recommendations: At least 80% of adherence for the following prescribed recommendations at 6 and 12 months:
 - Diet recommendations
 - Physical activity recommendations
 - Drug prescriptions:
 - o Aspirin for all without contraindications
 - o P2Y₁₂ inhibitors for all, according to the time indicated at discharge (if none, use 12 months)
 - o Statins / other lipid-lowering therapies for all
 - o Any of the following if indicated:
 - Beta blockers (if LVEF <0.40 or HF)
 - Angiotensin-converting enzyme inhibitors or angiotensin receptor blockers (if LVEF <0.40 or HF)
 - Glucose control medications (SGLT2 inhibitors/GLP-1 agonists)

1. Measurement of adherence to pharmacological recommendations:

a) The Morinsky Medication Adherence Scale (MMAS-8).⁷⁷ A total score of all items will be calculated with a sum score ranging from 0 to 8 for adherence. MMAS-8 Score will be calculated if the respondent answers at least 6 of 8 items. MMAS is trichomized in three levels of adherence:

- High adherence (score 8)
- Medium adherence (score, 6 to 7)
- Low adherence (score, <6)

b) Records of dispensations in the pharmacy: This is an indirect method to measure compliance based on evaluating the collection of the medication in the pharmacy. Patients who withdrew all medications during the year will be considered adherent. The information will be checked from the medical history that records the withdrawal of drugs from the pharmacy. This will be done for each of the secondary prevention medications to calculate adherence to each of them (aspirin, P2Y₁₂ inhibitors, statins, and beta blockers or ACE inhibitors).

2. Measurement of adherence to non-pharmacological recommendations:

c) Adherence to diet: to evaluate this measure, the 14-point Mediterranean Diet Adherence Screener (MEDAS) questionnaire of Schröder et al, (2011) will be used ⁷⁸. It is a 14-item questionnaire derived from the PREDIMED study (Primary Prevention Mediterranean Diet). Each item is assessed with a binary score (0 or 1) according to the diet pattern, referring to daily or weekly consumption, during the last 3 months. The score ranges between 0 and 14 points, establishing two levels of adherence:

- Score <9: Poor adherence to the Mediterranean Diet, which requires an improvement in eating habits.
- Score ≥9: Good adherence to the Mediterranean Diet

d) Adherence to physical activity: it will be used the International Physical Activity Questionnaire (IPAQ) (Craig, 2003) ⁷⁹. It consists of 5 questions about the frequency, duration and intensity (vigorous or moderate) of physical activity, carried out in the last week (last 7 days). It also collects the frequency and duration of the walking activity and the time that the person remains seated on a weekday. The IPAQ allows individuals to be assigned to three categories (low, medium, high)

according to the estimated energy expenditure for each activity: vigorous, 8 MET (metabolic equivalent task); moderate, 4 METs; and walking, 3.3 METs. According to the IPAQ categories, individuals who belong to the high or medium category are compliant, and those who belong to the low category are non-compliant. In addition to the classification by METs, there is the possibility of classifying individuals based on the duration, frequency and intensity of physical activity, without the need to calculate METs. These criteria included in the official guidelines published by the IPAQ Research Consortium are the following:

- Low – No activity reported or some activity reported, but not enough to meet Category 2 or 3.
- Moderate: any of the following 3 criteria
 - 3 or more days of vigorous activity of at least 20 minutes per day
 - 5 or more days of moderate-intensity activity and/or walking for at least 30 minutes per day
 - 5 or more days of any combination of moderate-intensity or vigorous-intensity walking activities, achieving a minimum of at least 600 METs/min per week.
- High: either of the following 2 criteria
 - Vigorous intensity activity on at least 3 days and accumulating at least 1500 MET-minutes/week
 - 7 or more days of any combination of walking, moderate or vigorous intensity activities that accumulate at least 3000 MET-minutes/week

e) Cardiac rehabilitation: Attendance to all cardiac rehabilitation sessions will be collected and those who have completed at least 80% of scheduled sessions will be considered adherent. To explore its influence on cardiac rehabilitation attendance, time from discharge to return to work will be collected as an outcome.

[figure not shown]
f) Measurement of clinical endpoints:

- Major adverse cardiovascular events at 6 and 12 months, including the combined endpoint of cardiovascular mortality, nonfatal AMI, nonfatal ischemic stroke
- Cardiovascular mortality
- Hospitalizations due to cardiovascular reasons
- Emergency department visits due to cardiac causes
- Urgent revascularization
- Acute myocardial infarction

g) The independent predictors of adherence with secondary prevention recommendations in women will be estimated with adequate statistical analyses (e.g., logistic regression models)

h) The use of healthcare resources will be analyzed using the COHERENT model⁸⁰.

Clinical Outcomes, HElthcare REsource UtilizatioN, and relaTED costs (COHERENT) Model

